#### 8.1.5 Outcome of Adverse Events

The Investigator will be asked to indicate the outcome of the AE using the following categories: Resolved without sequelae, Resolved with sequelae, Death, or Ongoing. The Investigator should use medical judgment to compare the reported AE to similar type events observed in clinical practice.

Below are the applicable guidelines for outcome assessment:

- Resolved without sequelae: the AE has resolved without residual symptoms
- Resolved with sequelae: the AE has resolved, however, residual consequences will persist
- Death: the AE ended with death
- Ongoing: the AE is not resolved yet

**JTA-KOA1 - Clinical Study Protocol**

JTA-KOA1-CSP

V 04

Author: EB

Date: May 10, 2017

Pg. 66/114

If the outcome of an AE is not available at the time of the initial report or at study exit (premature or not), follow-up will proceed until outcome is known. All collected data will be recorded in source documents.

### 8.1.6 Adverse Drug Reaction (ADR)

Adverse Drug Reaction (ADR): any untoward and unintended response to an investigational medicinal product related to any dose administered (having a reasonable causal relationship to the product, the term “reasonable causal relationship” meaning that there is evidence or arguments to suggest a causal relationship).

Unexpected ADR: an adverse reaction whose nature, severity, specificity, or outcome is not consistent with the applicable product information (e.g., Investigator’s Brochure)

### 8.1.7 Serious Adverse Reaction (SAR)

Serious Adverse Reaction (SAR): any untoward and unintended responses to an investigational medicinal product related to any dose administered (having a reasonable causal relationship to the product, the term “reasonable causal relationship” meaning that there is evidence or arguments to suggest a causal relationship), and that results in death, is life-threatening, requires patient hospitalization or prolongation of existing hospitalization, results in persistent or significant disability or incapacity, or is a congenital anomaly or birth defect.

## 8.2 Identifying Adverse Events

The occurrence of AE/SAE (related or not to product or study procedure) will be assessed by non-directive questioning of the patient from Visit #1, and each other visit searching for any changes in health status (e.g., "Have any adverse events, serious adverse events occurred since the last visit?") (see Table 7 below).

**JTA-KOA1 - Clinical Study Protocol**

JTA-KOA1-CSP	V 04	Author: EB	Date: May 10, 2017	Pg. 67/114
--------------	------	------------	--------------------	------------

**Table 7: Observation Period for the Occurrence of AE and SAE**

Start of Study AE/SAE Observation Period	Visit #1 (ICF signature)
End of Study AE/SAE Observation Period	6 months after treatment (Study completion)

Furthermore, any events volunteered by the patient during or between the follow-up visits, or detected through observation, physical examination (including vital signs), laboratory testing, or other clinical procedures during the observation period will be documented. Patients will be instructed that they must immediately report any AEs, complaints, or objective changes in their well-being to the Investigator or clinic personnel, regardless of the perceived relationship between the event and the investigational medicinal product.

In the event of an AE/SAE, the Investigator will immediately initiate appropriate therapy and management according to his/her medical judgment, and current good medical practice and will decide whether the patient must be withdrawn from the study or not. The patient must be followed up by additional examinations according to the medical judgment of the Investigator, until the AE/SAE and/or abnormal condition is resolved or the Investigator deems further observations or examinations are no longer medically indicated. Any medication administered for the treatment of an AE should be recorded in the patient's eCRF.

### **8.3 List of Foreseeable Adverse Events and Anticipated Adverse Drug Effects**

There are no known adverse events related to the use of JTA-004 products at this stage as the products have not yet been administered to humans. However, based on experiences from other HA preparations for knee OA, foreseeable adverse events related either to the product or to the procedures can be determined. A summary of foreseeable adverse events and their likely incidence based on clinical data from other HA-based viscosupplements is given in the Table 8 below:

## JTA-KOA1 - Clinical Study Protocol

JTA-KOA1-CSP

V 04

Author: EB

Date: May 10, 2017

Pg. 68/114

**Table 8: Summary of Foreseeable Adverse Events**

	AE	Likely Incidence*
Local AE	Arthralgia	1/10
	Joint stiffness	1/100
	Joint effusion	1/100
	Joint swelling	1/100
	Injection site pain	1/100
	Joint warmth	1/100
	Local haematoma	1/100
	Infectious complications	1/100
	Local skin reaction	1/100
	Pseudosepsis	1/10 000
	Injection site haemorrhage	1/10 000
Systemic AE	Back pain	1/100
	Cold symptoms (stuffy nose, sneezing, sore throat)	1/100
	Nausea	1/100
	Fatigue	1/100
	Paraesthesia	1/100
	Headache	1/1000
	Allergic reactions	1/10 000
Transient hypotension	Unknown	

\* Based on clinical data from other HA-based viscosupplements.

## 8.4 Reporting of Safety Issues

### 8.4.1 Reporting Events to the SSO by the Principal Investigator

All the following events are considered reportable events:

- any SAE
- new findings/updates in relation to already reported events

**JTA-KOAI - Clinical Study Protocol**

JTA-KOAI-CSP

V 04

Author: EB

Date: May 10, 2017

Pg. 69/114

All reportable events must be notified by the Investigator to the Study Safety Officer (SSO).

SAEs will be documented on the SAE Report containing a detailed written description of the event.

SAE Reports Forms should be completed, signed and sent by the Investigator not later than

**within 24 hours of event occurrence or awareness** to the SSO by e-mail [REDACTED]

[REDACTED] who will inform the Sponsor of the safety event occurrence.

Briefly, the SAE Report Form will include the following information and differentiated assessment:

- Patient Identification Number
- Investigation site and country
- Event: organ system
- SAE status and description
- Date of event onset and event resolution
- Outcome (recovery with or without sequelae, ongoing, death)
- Action taken (none, patient discontinuation and withdrawal from the study, change in concomitant medication(s) and/or new medication(s), inpatient hospitalisation or prolongation of existing inpatient hospitalisation, non-drug therapy given, other)
- Criteria for seriousness (death, life-threatening, medical or surgical intervention to prevent life-threatening illness or injury or permanent impairment to a body structure, permanent impairment of a body structure or a body function, new or prolonged hospitalisation, congenital abnormality or birth defect), and severity (mild, moderate, severe)
- Assessment of relationship to the investigational medicinal product (evaluated as yes, possibly, no)
- Assessment of relationship to procedures, including the treatment injection and blood sampling (evaluated as yes, possibly, no)

**JTA-KOA1 - Clinical Study Protocol**

JTA-KOA1-CSP	V 04	Author: EB	Date: May 10, 2017	Pg. 70/114
--------------	------	------------	--------------------	------------

#### 8.4.2 Reporting Events to ECs and Agencies by the SSO

The SSO is responsible for reporting SAEs received from Investigators to the ECs and Agencies, while blinding will be preserved for both Principal Investigators and Sponsor unless it is considered necessary in the interest of research patient safety.

Any SAE which indicates an imminent risk of death, serious injury, or serious illness and that requires prompt remedial action for other patients, users or other persons or a new finding are to be recorded and reported immediately, **but not later than 7 calendar days** after awareness by the SSO.

Any other reportable event as described above is to be recorded and reported immediately, **but not later than 15 calendar days** following the date of awareness by the SSO. The report must be provided to all Agencies relevant to all states in which the trial is taking place.

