**JTA- KOA1 - Clinical Study Protocol**

JTA-KOA1-CSP	V 04	Author: EB	Date: May 10, 2017	Pg. 22/114
--------------	------	------------	--------------------	------------

- **Storage:** maintenance of the investigational medicinal product under appropriate controlled conditions until administration
- **Study Protocol:** document that states the rationale, objectives, design and proposed analysis, methodology, monitoring, conduct and record-keeping of the clinical trial
- **Study Report:** document describing the design, execution, statistical analysis and results of a trial
- **Study Safety Officer (SSO):** individual designated to perform the handling, notification, and reporting of safety issues
- **Suspected Unexpected Serious Adverse Reaction (SUSAR):** serious adverse reaction, the nature, severity, specificity, or outcome of which is not consistent with applicable product information (e.g., the Investigator's Brochure)
- **Treated patient:** patient to whom a treatment has been administered

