The Investigator will immediately notify the Study Safety Officer and/or the Sponsor about the occurrence of any SAE and other relevant Serious Adverse Safety/Quality Events, in order to allow proper notification and reporting of these events to the CAs, ECs, and the other Investigators involved in the trial. Detailed description of Safety Data Notification, Reporting, and Management procedures is provided in Section 8).

The Sponsor (with or without the support from the Monitor) is responsible for submitting to the CAs and ECs any amendment to the Study Protocol, and any changes to the Patient Information Sheet and Informed Consent and/or Investigator's Brochure, for approval prior to implementation.

The Investigator will prepare and submit (with or without the support from the Monitor) annual reports to the CAs and ECs, and according to local regulations and guidelines. The Investigator (with support from the Study Safety Officer) must also provide the CAs and ECs with any reports of SAEs from the study site, as dictated by the CAs and ECs requirements.

The CAs and ECs will be notified by the Sponsor about the end of the trial within 90 days. If the trial is terminated earlier, the CAs will be notified within 15 days. A report summarising the study results will be sent to the CAs within one year after the end of the trial.

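### Section 8.4.2 makes action for other people a necessary condition for the 7-day limit, so a first report of a fatal or life-threatening suspected unexpected reaction can fall under the 15-day limit

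*Combined protocol and SAP*

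**What the plan says.** Section 8.4.1 lists two kinds of reportable event: any SAE, and "new findings/updates in relation to already reported events". The investigator has 24 hours to send the SAE form to the Study Safety Officer (SSO).

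Section 8.4.2 governs the next step, from the SSO to ethics committees and agencies. Its first rule covers "Any SAE which indicates an imminent risk of death, serious injury, or serious illness and that requires prompt remedial action for other patients"; the part after the *and* reads in full "requires prompt remedial action for other patients, users or other persons or a new finding", so it ends with the alternative of a new finding. Such reports are due immediately, "but not later than 7 calendar days" after the SSO becomes aware. Its second rule is the remainder: "Any other reportable event as described above is to be recorded and reported immediately", "but not later than 15 calendar days" after SSO awareness.

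The protocol has the vocabulary for a different rule. The Definitions of Terms describe a SUSAR as a "serious adverse reaction, the nature, severity, specificity, or outcome of which is not consistent with applicable product information". Section 8.1.2 lists death as an SAE outcome, and its notes define life-threatening as an immediate risk of death. Sections 8.1.6 and 8.1.7 define unexpected and serious reactions. Section 12.1 lists guidance on expedited reporting among the documents that the trial follows, without giving its timelines.

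**The concern.** The two conditions in the 7-day rule are joined by *and*. However grave the event, the shorter limit applies only if something must also be done promptly for other people, unless the report counts as a new finding. Whether others need action is a judgement that may not be settled when a first report arrives. A fatal outcome, relatedness and unexpectedness are not criteria for either limit, so an unrelated SAE and a fatal suspected unexpected reaction can share the 15-day limit.

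According to Sections 2.3 and 8.3, JTA-004 has not yet been given to humans, and Table 8 gives the likely incidence of transient hypotension as unknown. Early reports of grave suspected reactions carry the most information in that setting. The undefined new-finding trigger adds to the difficulty, because the SSO cannot tell from the text which follow-up items take the shorter limit.

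**Working it through.** No statistical calculation applies. The check treats the 8.4.2 sentence as a logical rule and runs cases through it.

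**Inputs**
- A: imminent threat to life or of serious harm to health (8.4.2).
- B: prompt action needed for other people (8.4.2).
- C: a new finding (8.4.2, undefined there; 8.4.1 pairs new findings with updates and ties both to events already reported).
- Limits: 7 days if the rule is met, otherwise 15 days, both counted from SSO awareness (8.4.2).

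**Two grammatical readings**
- Reading 1: 7 days if (A and B) or C.
- Reading 2: 7 days if A and (B or C).

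A death is not named in the sentence. The table takes the view most favourable to the plan and counts a fatal or life-threatening event as meeting A.

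| Case | A | B | C | Reading 1 | Reading 2 |
|---|---|---|---|---|---|
| 1. First report, fatal or life-threatening suspected unexpected reaction, no action needed for others | yes | no | no | 15 | 15 |
| 2. Same event, action needed for others | yes | yes | no | 7 | 7 |
| 3. Action needed for others, no imminent threat | no | yes | no | 15 | 15 |
| 4. New finding on an already reported event without imminent threat | no | no | yes | 7 | 15 |
| 5. Routine update on such an event, not regarded as a new finding | no | no | no | 15 | 15 |
| 6. Already reported event later proves fatal, regarded as a new finding | yes | no | yes | 7 | 7 |

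**Result.** Case 1 takes the 15-day limit on both readings. Cases 1 and 2 differ only in B, so B is what moves a first report of a grave reaction between limits. Case 3 shows that B alone does not earn 7 days either. Only case 4 depends on the reading.

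Case 1 would move to 7 days if a new finding were stretched to include a first unexpected reaction. The wording of 8.4.1, which concerns events already reported, does not support that.

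**Size.** From SSO awareness: 15 − 7 = 8 days. With the 24 hours allowed from site to SSO, the outer limits are 1 + 15 = 16 and 1 + 7 = 8 days, and the difference is still 8 days.

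**The case against.** Several points on the other side are sound and limit the claim.

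- A reader might infer that the limits ignore death and threat to life. They do not. Imminent risk of death is one of the alternatives in a required limb of the 7-day rule, close to the protocol's own meaning of life-threatening. The limb is necessary but not sufficient.
- A reader might infer that a mere update gets 7 days while a fatal reaction gets 15. That needs Reading 1 and also needs a new finding in 8.4.2 to absorb the updates of 8.4.1. The text permits this but does not say it. Case 6 shows that the same trigger also protects some grave events.
- Both rules ask for immediate reporting, so 7 and 15 days are outer limits. Section 11.9 also has the SSO inform agencies and ethics committees immediately of new events that may affect patient safety or the risk-benefit ratio, and a fatal possibly related reaction would plausibly qualify. This softens the gap without closing it: immediacy is common to both rules, so only the day counts distinguish them, and Section 11.9 sets none.
- A reader might infer that patients go on being injected because agencies hear late. Dosing is covered separately by the provision to postpone treatment (8.4.3), ongoing safety monitoring (8.4.4) and the data safety monitoring board (8.4.5).
- A reader might infer a conflict over who reports, since under Section 12.2 the investigator "must also provide the CAs and ECs with any reports of SAEs from the study site". That sentence describes a site-level duty, carried out with SSO support and as the authorities and committees require. It reads as supplementary, and duplicate or missed reports would be speculation.
- Sending every SAE to the authorities is broad, but not unsafe. Limits that applied to SUSARs only would leave other SAEs, which now have 15 days, with none.

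**Conclusion.** The concern holds as a drafting gap with a safety consequence. Under Section 8.4.2 as written, a first report of a fatal or life-threatening suspected unexpected reaction falls under the 15-day limit whenever no action for others is identified. The cost is up to 8 days in the outer limit; the actual delay may be much shorter or nil.

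The conclusion rests on reading *and* as a true conjunction and on taking a new finding to concern an event already reported, as 8.4.1 indicates. It does not depend on which grammatical reading is chosen. The documents give no expected number of such events, so the frequency cannot be estimated. They also do not state the timelines of the guidance cited in Section 12.1, so nothing is claimed here about compliance with it.

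**What to change.** Reword Section 8.4.2 as follows.

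1. A suspected unexpected serious reaction, as the protocol already defines it, that is fatal or life-threatening triggers the existing 7-day limit on its own.
2. Need for prompt action for other people becomes a separate, sufficient trigger for 7 days. Cases 1 and 3 above then both move from 15 to 7 days, and case 2 stays at 7.
3. The existing 15-day limit stays for all other reportable events, so that no SAE is left without a limit.
4. Define a new finding, say how it differs from an update, and state which limit follow-up information takes.
5. Check the result against the expedited-reporting guidance listed in Section 12.1 and cross-refer to the duty in Section 11.9.

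The cost is a wording change and a faster turnaround for a few events. The SAE form in 8.4.1 already records death, threat to life and relatedness. Expectedness is not among the items listed there, so the SSO would judge it against the product information named in the SUSAR definition.

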#### 8.4.3 Serious Adverse Event Stopping Rule

In case of SAE occurs, which have not been identified in nature, severity or frequency in this protocol or in the IB and, which are thought to be possibly related to investigational medicinal products and are considered to be a health risk for all participating patients, Bone Therapeutics S.A. may decide in consultation with the Investigators to postpone treatment of newly included patients until the Investigators and Bone Therapeutics S.A. have thoroughly investigated the event(s) and conclude that continuation of the trial is justified.

#### 8.4.4 Safety Data Monitoring

The occurrence of AEs and SAEs will be monitored during the whole study period on an ongoing basis by the SSO and the Sponsor. The Sponsor will also receive from the SSO a regular detailed updated listing of all AEs and SAEs.

#### 8.4.5 Data Safety Monitoring Board

A Data Safety Monitoring Board (DSMB) will be established to assess the safety and efficacy data endpoints at intervals. This board will recommend to the Sponsor whether to continue, modify or stop the trial. Further information concerning the DSMB can be found in the SAP.

**JTA-KOA1 - Clinical Study Protocol**

JTA-KOA1-CSP

V 04

Author: EB

Date: May 10, 2017

Pg. 71/114

## 8.5 Management of Safety Issues

### 8.5.1 Procedure in Case of Pregnancy

All pregnancies occurring during the trial (including both patient pregnancy and patient's partner pregnancy) will be systematically reported within 24 hours of diagnosis to the SSO and Monitor (a Pregnancy Form will be immediately completed, with subsequent urgent notification).

If there is a pregnancy during the study period, the patient must be followed and the outcome of pregnancy must be reported to the SSO and Monitor. Follow-up shall be conducted to obtain outcome information on all prospective reports.

Any pregnancy will be handled as an SAE regardless the relationship between the treatment and the event. Any complication arising during pregnancy will be recorded as an AE/ADE and will constitute a SAE if it fulfils any of the specified criteria for a SAE.

At the end of the pregnancy, whether that is full-term or premature, information on the status of the mother and child will be forwarded to SSO.

If the outcome of pregnancy is:

- Elective abortions without complications, they will be recorded, documented and reported to the SSO and Monitor, but they should not be handled as AE;
- Any spontaneous miscarriages or abortions for medical reasons, or congenital abnormalities or birth defects, will be recorded, documented, reported, and handled as SAE and full details will be requested.

### 8.5.2 Emergency Procedures

In case of SAE or any other safety event or medical concern, the following contact will be available (24/7 cover) for continuous support and assistance (SSO):

**Emergency and Safety Events Phone Number:** XXXXXXXXXX

The Investigator is responsible for ensuring that procedures and expertise are available to cope with medical emergencies during the study. Each patient will receive a "Patient Card" with the

**JTA-KOA1 - Clinical Study Protocol**

JTA-KOA1-CSP	V 04	Author: EB	Date: May 10, 2017	Pg. 72/114
--------------	------	------------	--------------------	------------

name and surname and the Patient Identification Number, Title and EudraCT Number of the study, type of treatment received and Name of the Sponsor. This card will also record the name, surname, full address, and phone number of the Investigator, the address and phone number of the Emergency Room of the Investigation Site, and the Emergency and Safety Events Phone Number (24/7 cover). The aim of this card is to inform any physician having to deal with a patient in an emergency situation that the patient is involved in a clinical trial and that he/she can contact the Investigator for more relevant information. Patients will be instructed to carry this card around at any time during the study.

For any other questions or study information, the following contact will be available (office hours) for continuous support and assistance:

*Hotline - Phone Number:* [REDACTED]

*Hotline - E-mail:* [REDACTED]

### **8.6 Long-Term Safety Reporting System**

Finally, during the course of the trial, the Sponsor plans to design, develop, and submit to the relevant CAs, a detailed strategy for long-term patient follow-up, under Pharmacovigilance Plan in line with the ICH Topic E2 E.

**JTA-KOAI - Clinical Study Protocol**

JTA-KOAI-CSP

V 04

Author: EB

Date: May 10, 2017

Pg. 73/114

**9 PREMATURE REMOVAL FROM THE STUDY****9.1 Reasons for Patient Premature Discontinuation**

Notification of patient study discontinuation (and reasons for discontinuation) will be communicated to the Monitor and/or the Sponsor by the Investigator as soon as possible. The Investigator will document the circumstances for premature discontinuation in the patient's eCRF as follows:

- ***Violation of eligibility criteria***

Patients will be withdrawn if incorrectly included (i.e., not in compliance with one or more eligibility criteria). The Investigator may contact the Monitor in order to discuss the potential continuation of wrongly included patients if judged that it is in the interest of the patient to continue the study.

In any case, and especially if the patient is withdrawn for safety reasons, the explanation for this discontinuation due to violation of eligibility criteria should be documented in the eCRF.

- ***Adverse Events / Serious Adverse Events***

Any patients may be withdrawn from the study at the Investigator's discretion in case of a safety concern. However, patients can be withdrawn from the study for AE/SAE (including notably clinical and/or laboratory events) only if the Investigator has clearly determined that the patient's withdrawal would reduce safety risks. In this case, the AE Page in the eCRF must be completed, explaining the rationale for withdrawal. In addition, the Investigator should ensure that adequate medical care and management will be provided to the patient.

- ***Withdrawn consent***

Participation in the study is strictly voluntary. A patient has the right to withdraw from the study at any time, and for any reason, without prejudice to further treatment, care, and patient-physician relationship. Under these circumstances, an adequate standard of care will always be adopted by the Investigator. The reason(s) for withdrawing consent will also be reviewed with the patient and documented in source documentation and the eCRF. Particularly, the patient must be carefully questioned for the possible occurrence of any AE/SAE.

JTA-KOA1 - Clinical Study Protocol				
JTA-KOA1-CSP	V 04	Author: EB	Date: May 10, 2017	Pg. 74/114

- ***Lack of compliance to the protocol***

The Investigator or the Sponsor can terminate the study at any time for non-compliant patients.

- ***Lost to follow-up***

Efforts must be made to re-contact patients who do not return for scheduled visits in order to, at minimum, determine health status and the potential occurrence of AE/SAE. All efforts to re-contact patients will be documented in the source documentation and the eCRF.

- ***Lack of efficacy***

Early discontinuation for lack of efficacy will not be considered as an AE but as a treatment failure. The reason of the lack of efficacy will be documented in the eCRF and source documents.

- ***Other reasons***

If no above-mentioned reasons are applicable in case of early discontinuation, the other reason(s) will be clearly documented and explained in the eCRF and source documents.

